9.2 Analysis Populations

9.2.1 Full Analysis Set (FAS)

Based on the Intent-to-Treat (ITT) principle, includes all randomized subjects who received at least one treatment session from either the experimental or control group.

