6.2 Concomitant Treatment and Follow-up Visits

All enrolled patients will receive standard post-PCI medication and strict secondary prevention for coronary artery disease.

Follow-up visits will occur at 4, 8, 12, and 16 weeks post-randomization. Follow-up content includes: HAMA, HAMD, BDI, GAD-7, PCL-C, and SF-36 scale assessments; HRV measurement; echocardiography; venous blood tests; assessment of smoking/alcohol cessation and lifestyle improvement; record of follow-up visits (time, location, results); presence of angina or heart failure-related symptoms; occurrence of MACE (time, management, outcome); adverse reactions.

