9.1 Sample Size Determination

This is a randomized controlled trial. Significance level (α) is set at 0.05, and power ($1-\beta$) at 0.80. Based on literature, the effect size for taVNS alleviating depression is approximately 57%. Using PASS software, the calculated sample size per group is $n_1=n_2=56$. Considering a 10% dropout/loss-to-follow-up rate and the need for stratification by age and gender, the minimum sample size per group is determined to be 60, resulting in a total sample size of 120.

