9.3 Efficacy Analysis and Statistical Methods

9.3.1 Analysis of Primary Endpoint

Comparison of HAMD scores between groups will be performed using t-tests or non-parametric tests.

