9.4 Safety Analysis and Statistical Methods

Statistical analysis will be performed using SPSS 26.0 software. Categorical data will be presented as counts and percentages. Normally distributed continuous data will be presented as mean \pm standard deviation; non-normally distributed continuous data will be presented as median and interquartile range. Differences between groups for normally distributed continuous data and categorical data will be compared using independent samples t-tests and chi-square tests, respectively. Non-parametric tests will be used for non-normally distributed continuous data. Bayesian analysis will be employed to further explore the impact of different stimulation modalities on outcome prognosis. All statistical tests will be two-sided, with a P-value <0.05 considered statistically significant.

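### The analysis set labelled ITT leaves out randomised patients with no session, and the named Week 8 test, if run on observed scores, risks a completer comparison that ignores the Week 4 HAMD

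*Protocol*

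**What the plan says.** - **Analysis set.** Protocol 9.2.1: "Based on the Intent-to-Treat (ITT) principle, includes all randomized subjects who received at least one treatment session". It requires one session. It does not require a Week 8 score.
- **Primary test.** Protocol 2.2.1 sets the primary endpoint as HAMD at Week 8. Protocol 9.3.1: "Comparison of HAMD scores between groups will be performed using t-tests or non-parametric tests".
- **Visits.** Protocol 6.2: "Follow-up visits will occur at 4, 8, 12, and 16 weeks post-randomization". HAMD is among the assessments listed for these visits, so a score is due halfway through the 8 weeks of treatment.
- **Leaving the trial.** Section 4.3 allows patients to leave to seek other treatment or for no given reason. Section 6.3 adds withdrawal for poor adherence (including stopping the device), for serious new illness and for loss to follow-up. Neither says whether such patients are still rated at Week 8.
- **Expected loss.** Protocol 9.1: "Considering a 10% dropout/loss-to-follow-up rate".
- **Blinding.** Section 5.1.2 has the telephone system tell the researcher which group the patient is in. Section 5.2 lists research personnel among those blinded.

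**The concern.** There are two separate weaknesses.

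First, the ITT label does not fit the definition. Excluding patients who had no session is easiest to defend when nobody can act on the allocation between randomisation and the first session. Here 5.1.2 and 5.2 disagree on whether the researcher knows the group, so it cannot be taken for granted that starting treatment is independent of arm.

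Second, a two-sample test of observed Week 8 scores uses one number per patient and only patients who have it. The text makes loss related to outcome plausible. Patients enter after declining antidepressants and psychotherapy (4.1), so a patient who is not improving has an obvious reason to leave for other treatment. The arms also differ in what patients feel: stimulation at the highest tolerable intensity in one, and 5 seconds per session in the other (6.1). Perceived benefit and tolerability could therefore drive loss differently by arm. If they do, the Week 8 difference is biased, while a Week 4 score that predicts part of the loss goes unused. Adjusting for baseline among completers alone does not cure this.

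**Working it through.** **1. The plan's own numbers.** The plan states two-sided alpha 0.05, power 0.80, an effect of about 57% on an unstated scale, 56 per group, and 60 per group after allowing for 10% loss. Reading 57% as a standardised difference of 0.57 (an assumption):

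n per group = 2 × (1.960 + 0.842)² / 0.57² = 15.70 / 0.3249 = 48.3, so 49 (50 with the t distribution).

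The 56 is not reproduced. Other readings of 57% come close to 56 but need inputs that the plan does not give, so 56 is not shown to be wrong. What matters here is the margin: 60 × 0.90 = 54 per group with a Week 8 score, below 56. Taking the effect that makes 56 exact (0.534 SD), power is 82.7% with 60 analysed per group, 78.5% with 54, and 73.6% with 48 (20% loss). At 0.57 SD the figures are 87.2%, 83.5% and 78.9%.

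**2. Bias by hand.** Let leavers be k SD worse at Week 8 than completers in the same arm.

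- Same k in both arms: completer bias = k × (loss in active − loss in sham). With equal loss it is 0. With a 10-point imbalance and k = 0.25 to 1.0 it is 0.025 to 0.10 SD.
- Outcome-related loss in one arm only: bias = k × loss in that arm. At 10% loss and k = 0.5 this is 0.05 SD, or 0.05 × 6 = 0.30 points if the SD is 6.

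**3. Bias by simulation.** All inputs are assumptions except 60 per arm and 10% loss: Week 4 and Week 8 SD 6; baseline SD 4.5; correlations 0.5 (baseline and Week 4), 0.45 (baseline and Week 8) and 0.7 (Week 4 and Week 8); true Week 8 effect 0.57 × 6 = 3.42 points; Week 4 effect 60% of that; all loss after Week 4. Loss rises with Week 4 HAMD in sham and is random in active. The result depends on how steeply loss rises:

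| Log-odds of loss per SD of Week 4 HAMD | t-test bias at 10% loss (points) |
|---|---|
| 0.5 | 0.22 |
| 0.8 | 0.30 to 0.31 |
| 1.0 | 0.37 |
| 1.5 | 0.48 to 0.54 |

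Ranges are results from separate runs. As a share of 3.42 points, 0.2 is 6% and 0.5 is 15%. In this scenario the benefit is understated. If active non-improvers are the ones who leave, the sign reverses.

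At slope 0.8, power of the t-test is 78% at 10% loss, against 83% when both arms leave by the same mechanism. Completer ANCOVA is still off by 0.22 points. A model using the Week 4 score is within about 0.07, even without baseline. At 20% loss, twice what the plan allows for, the t-test bias is 0.53 to 0.61 points and power is 63%, against 81%.

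**4. Same mechanism in both arms.** Bias is about 0. If the rule acts on the absolute Week 4 score, a small bias of 0.02 to 0.17 points remains at 10% loss, because treated patients score lower and so leave less often.

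**5. Never-starters.** The plan gives no figure. If 1 to 3 of 60 per arm never start (assumption), the set loses 1/60 to 3/60, about 2% to 5% of randomised patients.

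**The case against.** A reader might infer that the protocol drops everyone without a Week 8 score, so that the primary result is a completer comparison. The document does not say so. Section 9.2.1 keeps a patient with one session and no Week 8 score, and 9.3.1 contains no complete-case rule. A t-test can be run on imputed scores, and missing-data handling is commonly left to the SAP, which is not at hand. That silence is not a finding. Nor does the one-session rule create a completer set: it probably removes few patients, and it biases the comparison only if starting depends on the arm.

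The size is also open to challenge. It comes from assumed inputs and a one-sided mechanism. The model that uses Week 4 does well partly by construction, because loss was generated from the Week 4 score. Loss before Week 4, or loss driven by unobserved factors, would not be repaired. Under the null, the same scenario gives rejection rates of 6.0% and 8.2% at 10% and 20% loss, but about 67% to 97% of those rejections favour sham, so they are not mainly false claims of efficacy.

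All of this stands and limits the point. Three things remain. The ITT label does not match the definition. The protocol does not leave the primary method open: it names a test that, on observed scores, cannot use the Week 4 rating. And whether withdrawn patients are still rated is a matter of trial conduct that an SAP cannot supply afterwards.

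**Conclusion.** The point holds in limited form. The full analysis set is a modified ITT set under an ITT description, and this matters more here because 5.1.2 and 5.2 conflict on whether the researcher knows the group. The named primary test risks a completer comparison and leaves collected Week 4 data unused.

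The likely size is modest: roughly 0.2 to 0.5 HAMD points at the planned 10% loss if loss depends on the Week 4 score in one arm only, in either direction, and near 0 if both arms behave alike. These figures rest on the assumed SD of 6, the correlation of 0.7, an effect of 3.42 points, loss only after Week 4, and the assumed steepness of loss. They show what could happen and are not a forecast. The change should be made because it is cheap and the better method uses data already planned.

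**What to change.** - **9.2.1.** Replace with: *FAS: all randomised patients, analysed in the assigned arm.* If the one-session condition is kept, call the set modified ITT. The per-protocol set in 9.2.2 already serves the adherent-patient question.
- **9.3.1.** Replace with: *The Week 8 HAMD difference is estimated on the FAS from a likelihood-based repeated-measures model of HAMD at Weeks 4, 8, 12 and 16 with arm, visit, arm-by-visit, baseline HAMD and baseline-by-visit, unstructured covariance.* Alternatively, model baseline HAMD jointly as an outcome. Patients with only a baseline score are then formally included, though they add little on the Week 8 difference.
- **6.2 or 6.3.** State that patients who stop the device are still rated at the scheduled visits where they agree. This concerns data collection only, not who should stop treatment.
- **Sensitivity analyses.** Keep the two-sample test of observed Week 8 scores, and add an analysis that allows for data missing not at random.
- **5.1.2 and 5.2.** Reconcile who learns the allocation.

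Cost: a few sentences, slightly more analysis work, and some effort to rate patients who have stopped. No new patients or scheduled visits are needed. The model relies on data being missing at random given the observed HAMD scores. It does not remove bias from loss before Week 4 or from loss unrelated to the observed scores.

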9.2.2 Per Protocol Set (PPS)

Includes all subjects who completed the treatment regimen as specified in the protocol without major protocol violations. The exact definition of major protocol violations will be finalized during data review and may include (but is not limited to): failure to meet inclusion criteria, receipt of interfering treatments post-enrollment, poor adherence, visits outside specified time windows.

9.3 Efficacy Analysis and Statistical Methods

9.3.1 Analysis of Primary Endpoint

Comparison of HAMD scores between groups will be performed using t-tests or non-parametric tests.

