2.2 Study Endpoints (or Evaluation Metrics)

2.2.1 Primary Endpoint (or Primary Evaluation Metric) and Definition

Hamilton Depression Rating Scale (HAMD) score at Week 8: The 17-item HAMD is convenient, has clear criteria, is easy to master, and can be used to assess depressive symptoms in various conditions including depression, bipolar disorder, and neurosis, being particularly suitable for major depressive disorder.

Scoring criteria:

No depressive symptoms: Total score ≤ 7 ; Mild depression: Total score ≥ 8 and ≤ 17 ; Moderate depression: Total score > 17 and ≤ 24 ; Severe depression: Total score > 24 .

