4.1 Inclusion Criteria

- Age ≥ 18 years;
- Meets diagnostic criteria for ACS;

- 14 days to 12 months post-successful PCI, with stable vital signs;
- Meets Diagnostic and Statistical Manual of Mental Disorders, Fifth Edition (DSM-V) diagnostic criteria for Major Depressive Disorder;
- HAMD-17 score ≥ 7 and < 24 , with HAMA score $<$ HAMD score;
- After full disclosure of condition, the patient or legal representative refuses psychiatric consultation and declines antidepressant medication or psychotherapy;
- Patient or legal representative voluntarily participates in the study and provides written informed consent.

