5.1 Randomization

5.1.1 Method for Generating Random Allocation Sequence

Stratified block randomization will be used: Eligible patients will be randomly assigned to Group A or B in a 1:1 ratio. Using R software, stratification will be based on age (two levels: 18-60 years, >60 years) and gender (two levels: male, female), resulting in 4 strata. Within each stratum, patients will undergo randomization with varying block sizes. The output will determine the stimulation device assigned to each patient.

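### The primary Week 8 HAMD comparison is unadjusted: it uses neither baseline HAMD nor the age and sex strata, and the outcome data decide whether it is a mean or a rank comparison

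*Protocol*

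**What the plan says.** The primary endpoint (Protocol 2.2.1) is the "Hamilton Depression Rating Scale (HAMD) score at Week 8", that is, the score itself and not the change from baseline. The analysis in 9.3.1 is one sentence: "Comparison of HAMD scores between groups will be performed using t-tests or non-parametric tests".

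The rule for choosing the test stands in 9.4, under the safety heading. For the parametric case: "Differences between groups for normally distributed continuous data and categorical data will be compared using independent samples t-tests and chi-square tests, respectively". For the other case: "Non-parametric tests will be used for non-normally distributed continuous data". The section sets no criterion for normality and does not name the non-parametric test.

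Randomization (5.1.1) is 1:1 in blocks within strata: "stratification will be based on age (two levels: 18-60 years, >60 years) and gender (two levels: male, female), resulting in 4 strata". Section 9.1 cites this stratification again when it sets the sample size.

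Entry (4.1) requires "HAMD-17 score ≥ 7 and < 24", and HAMD is listed in the baseline table in 10.1. No section mentions a covariate, an ANCOVA, a mixed model or a stratified test.

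**The concern.** Three pieces of information are at hand before treatment starts, and the primary test uses none of them.

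- **Baseline HAMD.** The endpoint is a raw Week 8 score, so baseline does not enter even through a change score. Baseline HAMD does not stratify the randomization either, so neither design nor analysis takes account of it. If it predicts Week 8 HAMD, its variation stays in the residual error.
- **Age and sex.** Stratifying balances these factors between arms. A test that ignores them then overstates the standard error to the extent that they are prognostic.
- **Form of the result.** A t-test compares means and a rank test compares orderings. Because 9.4 decides between them by the distribution of the outcome, the quantity that the primary result estimates is not fixed until the data are seen.

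This is not a detail left to a statistical analysis plan. The protocol itself names the unadjusted test, and a later plan using ANCOVA would have to depart from it.

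**Working it through.** **Inputs from the protocol.** Alpha 0.05 and power 0.80 (9.1), two-sided (9.4); effect size approximately 57%, not further defined (9.1); 56 per group calculated, 10% dropout, 60 per group planned (9.1).

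**Assumed input.** The correlation r between baseline and Week 8 HAMD is not in the protocol. Values of 0.2, 0.3, 0.5 and 0.6 are used.

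**Step 1. The plan's own figure.** Reading 57% as a standardized difference d = 0.57, the normal formula gives n = 2 × [(1.960 + 0.842)/0.57]² = 48.3, so 49 per group; the t-based calculation gives 49.3, so 50. The stated 56 is not reproduced on this reading. Two effects are therefore carried forward:
- d = 0.534, the effect that a t-test with 56 per group detects with 80% power;
- d = 0.57, the stated figure taken as a standardized difference.

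**Step 2. Evaluable patients.** 60 × (1 − 0.10) = 54 per arm.

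**Step 3. Effect of adjusting for baseline.** ANCOVA multiplies the residual variance by (1 − r²), so the effect in residual SD units becomes d/√(1 − r²). Power comes from the noncentral t distribution with 106 degrees of freedom and noncentrality [d/√(1 − r²)] × √(54/2). For d = 0.534 and r = 0 the noncentrality is 0.534 × 5.196 = 2.775, and power is 78.5%.

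| r (assumed) | Residual variance, 1 − r² | Power, d = 0.534 | Power, d = 0.57 |
|---|---|---|---|
| unadjusted | 1.00 | 78.5% | 83.5% |
| 0.2 | 0.96 | 80.1% | 85.0% |
| 0.3 | 0.91 | 82.2% | 86.8% |
| 0.5 | 0.75 | 88.8% | 92.3% |
| 0.6 | 0.64 | 93.0% | 95.6% |

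Three covariates (baseline, age stratum, sex) leave 108 − 5 = 103 degrees of freedom, which changes these powers by less than 0.1 percentage point. No gain is credited to age and sex, because the protocol gives nothing from which to size it.

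**Step 4. Data-dependent choice of test.** Type I error was simulated with 54 per arm and 20,000 runs, for normal and for skewed (gamma) data. If a Shapiro-Wilk test decides between the t-test and the Mann-Whitney test, the error is 0.049 (normal) and 0.050 (skewed). If the more favourable of the two could be picked, it is 0.058 and 0.067.

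**The case against.** Four stronger readings are tempting, and the documents support none of them.

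- **The primary test is biased or invalid.** It is neither. Under 1:1 randomization the unadjusted comparison is unbiased, and its standard error already allows for chance baseline imbalance. Ignoring prognostic strata makes the test conservative.
- **The analyst may report whichever test looks better.** Section 9.4 gives a rule, and its wording is general although it stands under safety. The error of 0.058 to 0.067 arises only if that rule is not followed; with a formal normality gate, type I error is about 0.05. What stands is narrower: no normality criterion, no named rank test, and a result whose form depends on the outcome data.
- **A rank test would leave no estimate in HAMD points.** A Hodges-Lehmann shift with its confidence interval provides one. The protocol simply does not ask for it.
- **The unadjusted test leaves the trial short of 80% power.** That holds for d = 0.534. With d = 0.57 the unadjusted power is 83.5% even after dropout. If 57% is a response proportion, it implies no standardized HAMD difference at all.

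It is also fair to say that the size of the gain rests on an assumed correlation, and that the restricted entry range may keep r low. At r = 0.3 the gain is under 4 percentage points. None of this answers the core point: baseline HAMD and the strata are available, and the stated analysis does not use them.

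**Conclusion.** The point holds as a loss of precision and loose pre-specification, and it should be changed. For r from 0.2 to 0.6, adjustment adds about 2 to 15 percentage points of power if d = 0.534 (78.5% to between 80.1% and 93.0%) and about 1 to 12 points if d = 0.57 (83.5% to between 85.0% and 95.6%). These figures assume 54 evaluable patients per arm, a linear relation between baseline and Week 8 HAMD, and a correlation that the protocol does not supply. The direction is secure whenever r is not close to zero; the size is not known. The further gain from age and sex is unquantified, and is nil if neither is prognostic.

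**What to change.** Replace the sentence in 9.3.1 with one named primary model, for example: *Week 8 HAMD in the FAS is analysed by ANCOVA with treatment, baseline HAMD, age stratum and sex, reporting the adjusted mean difference and 95% CI.*

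Keep one named rank test, Wilcoxon-Mann-Whitney with the Hodges-Lehmann shift, as a sensitivity analysis only, and remove the normality rule from the choice of the primary analysis. Do not offer a mixed model as an interchangeable alternative: when Week 8 scores are missing, the two models use different patients and rest on different assumptions, so listing both would reopen the choice.

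Use the same baseline-adjusted model for the continuous secondary endpoints, with a log transformation for skewed biomarkers and HRV power measures.

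The cost is a protocol wording change, to be made before unblinding, and a few lines of SPSS. No additional patients, visits or measurements are needed.

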9.3.2 Analysis of Secondary Endpoints

Comparisons of HAMA scores, BDI scores, GAD-7 scores, PCL-C scores, SF-36 scores, HRV parameters, echocardiography parameters, and blood biomarkers between groups will be performed using t-tests or non-parametric tests. Comparison of HAMA response rates, remission rates, and MACE incidence between groups will be performed using chi-square tests.

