2.1 Study Aims

Aim 1: To compare the improvement in depression, anxiety, and quality of life between patients receiving transcutaneous auricular vagus nerve stimulation or sham stimulation using a randomized controlled design.

Aim 2: To compare the improvement in multiple physiological indicators between patients receiving transcutaneous auricular vagus nerve stimulation or sham stimulation using a randomized controlled design.

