7. Quality of Life Scale (SF-36) score: The 36-Item Short Form Health Survey (SF-36) is widely used, covering 8 domains: physical functioning, role-physical, bodily pain, general health, vitality, social functioning, role-emotional, and mental health. Patients are scored on quality of life to assess changes in physical, energetic, emotional, and mental health, using a percentage system. Higher scores indicate better function and quality of life.

8. Heart Rate Variability (HRV): A 10-minute resting ECG is recorded. HRV analysis methods mainly include time-domain, frequency-domain, and non-linear methods.

Key time-domain parameters include:

SDNN (Standard Deviation of all Normal-to-Normal [NN] intervals): Reflects overall autonomic nervous system activity, primarily sympathetic tone. Normal value (141 ± 39) ms; lower values suggest increased sympathetic activity and reduced adaptability.

- SDANN (Standard Deviation of the Averages of NN intervals in all 5-minute segments): Evaluates sympathetic nervous system activity. Normal value (127 ± 35) ms.

- rMSSD (Root Mean Square of Successive Differences between adjacent NN intervals): Reflects parasympathetic (vagal) activity. Normal value (27 ± 12) ms.

- pNN50 (Percentage of adjacent NN intervals differing by >50 ms): Lower values indicate lower parasympathetic activity.

Frequency-domain indicators include:

- Total Power (TP) (≤ 0.4 Hz): Reflects overall autonomic nervous system activity and regulatory capacity.
 - High Frequency (HF) (0.15–0.40 Hz): A good indicator of parasympathetic (vagal) function, influenced by respiration depth.
 - Low Frequency (LF) (0.04–0.15 Hz): Controlled by both sympathetic and parasympathetic systems; some studies consider it influenced by sympathetic activity, serving as a reliable indicator of cardiac sympathetic activity, affected by baroreflexes.
 - Very Low Frequency (VLF) (0.003–0.040 Hz)
 - Ultra-Low Frequency (ULF) (≤ 0.003 Hz)
 - LF/HF ratio: Reflects the balance of sympathetic-parasympathetic tone.
9. Echocardiography: Includes left ventricular anterior-posterior diameter (diastolic/systolic) and left ventricular ejection fraction (LVEF).
10. Venous blood biomarkers: Levels of N-terminal pro-B-type natriuretic peptide (NT-proBNP), interleukin-1 (IL-1), interleukin-6 (IL-6), tumor necrosis factor-alpha (TNF- α), high-sensitivity C-reactive protein (hs-CRP).

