10.1 Case Report Form / Electronic Data Record

Table 1: Baseline Characteristics

Gender(%)	Male Female	Age ,mean (SD), y	
Marriage status(%)	Single Married	BMI (kg/m ²)	
Residential Area(%)	Urban Rural	Living alone(%)	Yes No
Education(%)	Primary education Secondary School Technical secondary school or higher	Occupation(%)	Retired Unemployed Employed
cigarette(%)	Yes No	Participant consumes alcoholic beverages(%)	Yes No
Type of health insurance(%)	New rural cooperative medical scheme Urban Employee Basic Medical Insurance Uninsured	Previous PCI.or CABG events(%)	Yes No

Previous cardiac events(%)	Yes No	Diagnosticn (%)	NSTEMI UA STEMI
Previous PCI.or CABG events(%)	Yes No	Hypertension(%)	Yes No
Diabetes(%)	Yes No	Yes No	Yes No
hsCRP (mg/L)		Total implanted stents mean (SD), pc	
NYHA_Class(%)	I II	EF (%)	
IL-1 (pg/ml)		IL-6 (pg/ml)	
TNF- α (pg/ml)		LVD (d/s)	
HAMA		HAMD	
BDI		GAD-7	
SF-36		PCL-C	
HbA1c (%)		HRV (SDNN) (ms)	
HRV (SDANN) (ms)		HRV (RMSSD) (ms)	
HRV (TP) (Hz)		HRV (HF) (Hz)	

HRV (LF) (Hz)		HRV (VLF) (Hz)	
HRV (ULF) (Hz)		NT-proBNP (ng/mL)	
hsCRP (mg/L)			

Note: BMI: Body Mass Index; NSTEMI: Non-ST-Elevation Myocardial Infarction; UA: Unstable Angina; STEMI: ST-Elevation Myocardial Infarction; PCI: Percutaneous Coronary Intervention; CABG: Coronary Artery Bypass Grafting; LVEF: Left Ventricular Ejection Fraction; NT-proBNP: N-terminal pro-B-type Natriuretic Peptide; hs-CRP: High-sensitivity C-Reactive Protein; IL-1: Interleukin-1; IL-6: Interleukin-6; TNF- α : Tumor Necrosis Factor-alpha; LVD (d/s): Left Ventricular Diameter (diastolic/systolic); HAMA: Hamilton Anxiety Rating Scale; HAMD: Hamilton Depression Rating Scale; BDI: Beck Depression Inventory; GAD-7: Generalized Anxiety Disorder 7-item; SF-36: 36-Item Short Form Health Survey; PCL-C: PTSD Checklist-Civilian Version; HRV: Heart Rate Variability; HbA1c: Glycated Hemoglobin; SDNN: Standard Deviation of NN intervals; RMSSD: Root Mean Square of Successive Differences; TP: Total Power; HF: High Frequency; LF: Low Frequency; VLF: Very Low Frequency; ULF: Ultra-Low Frequency.*

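### Section 9.3.2 fixes unadjusted tests for the continuous secondary endpoints although baseline values are recorded for nearly all of them, which costs power and leaves the rank-test branch without an effect estimate

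*Protocol*

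**What the plan says.** Aim 2 in section 2.1 of the protocol is "To compare the improvement in multiple physiological indicators" between active and sham stimulation. Section 2.2.2 lists these indicators as secondary endpoints: heart rate variability (HRV), echocardiography, and blood markers (NT-proBNP, IL-1, IL-6, TNF-alpha, hs-CRP). Section 6.2 schedules them at four visits: "Follow-up visits will occur at 4, 8, 12, and 16 weeks post-randomization".

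For the analysis, section 9.3.2 says that comparisons of the scale scores and of "HRV parameters, echocardiography parameters, and blood biomarkers between groups will be performed using t-tests or non-parametric tests". Section 9.4 makes the choice depend on distribution: independent-samples t-tests for normal data, and otherwise "Non-parametric tests will be used for non-normally distributed continuous data". For the latter, "non-normally distributed continuous data will be presented as median and interquartile range".

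No baseline covariate, stratification factor, transformation, between-group estimate or confidence interval is named. Nor is it said whether the tested quantity is the follow-up value or the change.

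Section 10.1, under "Table 1: Baseline Characteristics", lists the five blood markers, ejection fraction, left ventricular diameter, the rating scales, SF-36, and the HRV measures SDNN, SDANN, RMSSD, TP, HF, LF, VLF and ULF. LF/HF follows from two of these. pNN50, a parameter in section 2.2.2, is not listed.

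**The concern.** A patient's own baseline is often the strongest predictor of a later value of the same measure. A two-group test that leaves it out keeps predictable between-patient variation in the error term. The protocol records the baseline and then names a method that does not use it as a covariate. The stratification factors of section 5.1.1, age and gender, are left out too.

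The second issue is estimation. Where data are judged non-normal, the plan gives a rank-test P-value beside two group medians with interquartile ranges. That says whether the groups differ, but it does not give the size of the difference with its uncertainty, which a reader of Aim 2 will want.

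At stake are power and precision in the secondary endpoints. The error rate of the planned tests is not in question.

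**Working it through.** **Inputs from the protocol.** 60 per group and 10% loss (section 9.1), so 60 × 0.9 = 54 analysed per arm; two-sided 0.05 (section 9.4); 1:1 allocation (section 5.1.1). The calculation in section 9.1 concerns depression. No planned figure exists for the physiological endpoints, so there is none to reproduce.

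**Assumptions, not in the protocol.** A positive marker that is normal on the log scale with SD 1.0; a true active-to-sham ratio of 0.65; a baseline-to-follow-up correlation r on the log scale, shown over a range.

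**Step 1: effect on the log scale.** −ln(0.65) = 0.431, which is 0.431 SD.

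**Step 2: rank test on follow-up values.** Ranks do not change under the log. Relative to a t-test on logs, the large-sample efficiency is 3/π = 0.955, so the working effect is 0.431 × √0.955 = 0.421. With 54 per arm the noncentral t gives 58% power. Simulation with 4,000 trials per setting gives 57–59%.

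**Step 3: ANCOVA on logs.** Residual variance is multiplied by 1 − r², so the working effect is 0.431/√(1 − r²). This ignores the few degrees of freedom spent on covariates and any gain from the strata.

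| r | 1 − r² | working effect | power, formula | power, simulation |
|---|---|---|---|---|
| 0 | 1.00 | 0.431 | 60% | 60% |
| 0.3 | 0.91 | 0.452 | 64% | 64% |
| 0.5 | 0.75 | 0.497 | 73% | 72% |
| 0.7 | 0.51 | 0.603 | 87% | 86% |

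Against 58%, the gain is about 2 points at r = 0 (from the log scale alone), 6 at 0.3, 14 at 0.5 and 29 at 0.7. Relative to an unadjusted log-scale comparison, the interval narrows by the factor √(1 − r²): 0.95, 0.87 and 0.71 at r = 0.3, 0.5 and 0.7.

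**Step 4: the change-score reading.** If the tests are applied to changes on the raw scale, simulated power at r = 0.3, 0.5 and 0.7 is 35%, 45% and 65% for the rank test, and 24%, 31% and 43% for the t-test. The most generous version is a t-test on log changes, which the protocol does not name. Its variance factor is 2(1 − r) = 1.4, 1.0 and 0.6, giving 47%, 60% and 82%. All are below ANCOVA at the same r.

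**Step 5: the t-test branch, for normally distributed endpoints.** Here no skewness assumption is needed. With 54 per arm and 80% power, an unadjusted comparison of follow-up values detects 0.544 SD. Multiplying by √(1 − r²) gives 0.52, 0.47 and 0.39 SD for ANCOVA at r = 0.3, 0.5 and 0.7.

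**Step 6: validity.** In a parallel log-normal simulation without a treatment effect, rejection rates were 4–5% for the raw t-test, the rank test, the log t-test and log ANCOVA alike.

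**The case against.** The strongest case against is that the named tests are valid, that these are secondary endpoints for which no power is claimed, and that covariates, transformations and effect measures are commonly settled in a SAP, which may exist. Validity stands. The SAP argument stands in part: an effect estimate for the rank branch could be supplied there. But the protocol is not silent on the method. It names unadjusted tests, and a SAP that made ANCOVA the main analysis would depart from it.

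The size is also open to challenge. No SD, ratio or correlation is documented, and at r = 0.3 or below the gain is 6 points or less. That stands, and is why the range is shown from zero.

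A reader might infer more than the text supports:
- That the tests ignore improvement because they compare follow-up values. Section 9.3.2 does not say so; tests on changes fit its wording.
- That the plan yields no estimate of improvement. For the t-test branch this is wrong: under randomisation the difference in follow-up means estimates the same effect as the difference in mean changes.
- That the fair comparator for a skewed marker is a raw t-test, at about 43% power under the same assumptions. Section 9.4 sends non-normal data to a rank test, so 58% is the comparator.
- That the protocol describes these markers as skewed. It only provides for non-normal data.
- That entry from 14 days to 12 months after PCI inflates the error term. That holds only so far as baseline differences persist to follow-up, which is not documented.

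**Conclusion.** The point holds as a matter of efficiency and estimation. Section 9.3.2 fixes an unadjusted comparison, leaves open whether values or changes are compared, and does not use baselines that section 10.1 records for nearly every endpoint concerned. Some power is lost under either reading whenever baseline and follow-up correlate positively, except that a change score approaches ANCOVA as r nears 1.

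Under the stated assumptions, power is about 58% for the rank test against about 64%, 72% and 87% for log-scale ANCOVA at r = 0.3, 0.5 and 0.7, with almost no difference near r = 0. The direction does not depend on skewness; the figures do depend on the assumed ratio, SD and r. The rank branch as written also specifies no between-group estimate or interval. None of this makes the planned tests invalid. Section 9.3.1 treats the primary HAMD comparison in the same unadjusted way, so one amendment could cover both.

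**What to change.** In section 9.3.2:
- Analyse each continuous secondary endpoint that has a baseline value by ANCOVA, with that baseline value, age stratum and sex as covariates, at the visit or visits the protocol designates for it.
- For positive measures that prove right-skewed (expected, though not documented, for the blood markers and HRV spectral powers), use logs of both outcome and baseline, and report the ratio of geometric means with 95% CI. For the others, report the adjusted mean difference with 95% CI.
- Keep the rank test as a sensitivity analysis, including for markers with many results below the assay limit, which ranks handle as ties.
- Add pNN50 to the baseline table if it is to be analysed in the same way; otherwise analyse it without baseline adjustment.

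The cost is wording and a little programming before unblinding, with no extra patients. The small downside is that the handling of values below the assay limit must be prespecified before logs are taken, since fixed substitution can bias a geometric-mean ratio.
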